5.3. Dose and Schedule Modifications

5.3.1. Dose and Schedule Modifications for TAS-120

5.3.1.1. General Considerations

This section defines general dose modification guidelines for patients receiving TAS-120 in any cohort. For detailed discussion of TAS-120 dose modification in Cohort 4 in the setting of a DLT, see Section 3.1.

In Cohort 4, in cases where a toxicity cannot be clearly attributed to either drug (TAS-120 or fulvestrant), TAS-120 should be modified or discontinued first.

The starting dose of TAS-120 is

- 20 mg QD for all patients in Cohorts 1-3
- 16 or 20 mg QD in Cohort 4, depending on the observations in the safety lead-in (Section 3.1).

Dose reduction to a minimum dose of 12 mg QD is permitted, with available dose levels of 16 mg QD and 12 mg QD.

If dose reduction fails to result in achieving minimal criteria to resume treatment, or if toxicities occur which would necessitate reduction of the dose of TAS-120 below 12 mg QD, the patient should be discontinued from TAS-120.

If the TAS-120 dose is reduced, the dose will not be increased upon resumption. If a benefit/risk assessment favors the increase of dose up to the initial starting dose after dose reduction, an agreement with the Sponsor's Medical Monitor is required prior to the dose increase.

If toxicities requiring dose reduction do not recover based on the criteria defined in Table 4 through Table 6 within 28 days after the last dose of TAS-120, the patient will be discontinued permanently from the study (Section 4.4). If resumption criteria are met within 28 days of the last dose of TAS-120, the patient may resume TAS-120 treatment at the appropriate dose level.

5.3.1.2. Dose Modifications for Nonhematologic Toxicities

Dosing modification guidelines for nonhematologic toxicities are provided in Table 4.

It is highly recommended to follow these guidelines, however, at the discretion of the Investigator, patients may continue on TAS-120 at the same dose without reduction or interruption for AEs (irrespective of grade) if the AE is considered unlikely to become serious or life threatening (including but not limited to fatigue and dry skin).

If there is any uncertainty about continuing therapy or resuming therapy in a patient with Grade \geq 3 nonhematologic AEs, the case must be discussed with the Sponsor's Medical Monitor prior to continuing TAS-120.

Table 4: TAS-120 Dosing Modification for Related Nonhematologic Toxicities

Grade	Dose Interruption/Resumption	Dose Adjustment
Grade 1 or 2	Maintain treatment at the same dose level, except for Grade 2 elevations of bilirubin, AST, and ALT, which should be managed as described in Table 7	None
Grade 3	Hold treatment until return to baseline or Grade ≤1	Reduce by 1 dose level from the previous level, except for Grade 3 nausea and/or vomiting controlled by aggressive antiemetic therapy or Grade 3 diarrhea responsive to antidiarrheal medication which does not require a dose hold or reduction.
Grade 4	Discontinue treatment	Permanent discontinuation of TAS-120.
Grade 4 (lab abnormality AE)	Hold treatment	TAS-120 will be permanently discontinued if assessed by the Investigator as life threatening. If it is in the best interest of the patient to continue treatment in the opinion of the Investigator and after discussion with the Sponsor, the patient can continue treatment at a reduced dose level. However, TAS-120 should first be held until toxicity returns to baseline or Grade ≤1.

Abbreviations: ALT=alanine aminotransferase; AST=aspartate aminotransferase.

Recommendations for hyperphosphatemia management are provided in Table 5. These are suggested guidelines based on emerging data from studies evaluating FGFR inhibitors, and from the experience of Investigators participating in ongoing studies of TAS-120. However, clinical judgment from treating physicians and local standard practices should be followed to decide the best management for each individual patient.

Table 5: Recommendations for Hyperphosphatemia Management

Serum Phosphorus Result ^a	Grade ^c	TAS-120 Dose Interruption and Modification
(mg/dL and mmol/L) ^b		Recommended Phosphate Binder for Management of Hyperphosphatemia ^d
ULN < P <5.5 (mg/dL) ULN < P <1.78 (mmol/L)	Grade 1	 No interruption, consider phosphate binder once serum phosphorus level is > ULN. Should serum phosphorus level rapidly increase within 1 week, consider early phosphate-lowering therapy, eg, Sevelamer tablets 800 mg three times per day [TID].
$5.5 \le P \le 7.0 \text{ (mg/dL)}$ $1.78 \le P \le 2.26 \text{ (mmol/L)}$	Grade 2	 No interruption, implement phosphate binder (monotherapy or in combination), Start with Sevelamer monotherapy (range from 800 mg TID to 2400 mg TID). Re-assess serum phosphate within 7 days, and plan to escalate Sevelamer or add treatment with acetazolamide 250 mg QD or TID and/or lanthanum carbonate (Fosrenol®) 1.0 g QD or TID, and further titratione, if phosphate level continues to increase.
7.0 < P ≤10.0 (mg/dL) 2.26< P ≤3.23 (mmol/L)	Grade 3	 Dose reduce TAS-120 to the next lower dose level and intensify phosphate lowering therapy If the serum phosphorus level has resolved to ≤ Grade 2 within 14 days after dose reduction, continue TAS-120 at the reduced dose level. If the serum phosphorus level has not resolved to ≤ Grade 2 after 14 days, further reduce TAS-120 from the last reduced dose level (or no lower than 12 mg QD). If the serum phosphorus level has not resolved to ≤ Grade 2 after 14 days of the second dose reduction of TAS-120 (or no lower than 12 mg QD), interrupt dosing with TAS-120 until it is resolved to ≤ Grade 2 before resuming TAS-120 at the reduced dose prior to dose interruption.
P > 10.0 (mg/dL) P > 3.23 (mmol/L)	Grade 4	• Interrupt TAS-120 until it's resolved to ≤ Grade 2, then resume TAS-120 at the next lower dose level and intensify phosphate lowering therapy. If after 2 dose interruptions and 2 dose reductions the serum phosphorus level has not resolved to ≤ Grade 2 after 14 days, permanently discontinue TAS-120.

Abbreviations: P=phosphorus; QD=once a day; TID=three times a day; ULN=upper limit of normal

- a. Serum phosphorus will be tested 4 days (± 24 hours) after Day 1 of Cycle 1 to initiate early intervention for hyperphosphatemia if indicated.
- b. $\text{mmol/L} = \text{mg/dL} \times 0.3229$ (conversion factor).
- c. This grading for the range of serum phosphorus levels will be used for the protocol.
- d. Phosphate binders can be used as monotherapy or in combination. Please consult the drug package insert. Sevelamer should be preferably taken in the middle of meals, both tablets and powder, in order to improve gastrointestinal tolerance and compliance. If Sevelamer cannot be used, other phosphate binders or hyperphosphatemia treatment drugs can be used. Lanthanum carbonate should be taken instead just after meals tablets of Fosrenol® are quite big, but can be cut if required. No dose adjustments are needed in patients with renal or hepatic impairment.
- e. Titrate the dose every 2-3 weeks until an acceptable serum phosphate level is reached.

5.3.1.3. Dose Modifications for Hematologic Toxicities

Criteria for dose interruption and resumption for hematologic toxicities are presented in Table 6.

Table 6: TAS-120 Dose Interruption and Modification Criteria for Related Hematologic Toxicities

Worst toxicity	Recommended dose modification any time during a cycle
CTCAE Grade (value)	of TAS-120
Anemia (Hgb)	
Grade 1 (Hgb < LLN - 10.0 g/dL)	Maintain dose level
Grade 2 (Hgb $< 10 - 8.0 \text{ g/dL}$)	Maintain dose level
Grade 3 (Hgb < 8.0 - 6.5 g/dL)	Withhold dose until resolved to \leq Grade 1 or baseline,
	 If resolved ≤7 days, then maintain dose level
	• If resolved >7 days, then reduce 1 dose level
Grade 4 (life threatening consequences; urgent intervention indicated)	Withhold dose until resolved to \leq Grade 1 or baseline, then reduce 1 dose level
Neutropenia (ANC)	
Grade 1 (ANC < LLN - 1500/mm ³)	Maintain dose level
Grade 2 (ANC < 1500 - 1000/mm ³)	Maintain dose level
Grade 3 (ANC $< 1000 - 500/\text{mm}^3$)	Maintain dose level
Grade 4 (ANC < 500/mm ³)	Withhold dose until resolved to \leq Grade 2 or baseline,
	 If resolved ≤7 days, then maintain dose level
	• If resolved >7 days, then reduce 1 dose level
Febrile neutropenia (ANC < 1000/mm ³ , fever ≥ 38.5°C)	Withhold dose until resolved, then reduce 1 dose level
Thrombocytopenia	
Grade 1 (PLT < LLN - 75,000/mm ³)	Maintain dose level
Grade 2 (PLT < 75,000 - 50,000/mm ³)	Maintain dose level
Grade 3 (PLT < 50,000 - 25,000/mm ³)	Withhold dose until resolved to \leq Grade 1 or baseline,
	• If resolved ≤7 days, then maintain dose level
	• If resolved >7 days, then reduce 1 dose level
Grade 4 (PLT < 25,000/mm ³)	Withhold dose until resolved to ≤ Grade 1 or baseline, then
	reduce 1 dose level

Abbreviations: ANC=absolute neutrophil count; CTCAE=Common Terminology Criteria for Adverse Events; Hgb=hemoglobin; LLN=lower limit of normal; PLT=platelets.

5.3.1.4. Adverse Event Follow-Up

All treatment-emergent AEs should be followed until resolution/stabilization or initiation of new anticancer therapy according to Table 7.

Table 7: Required Follow-up for Adverse Events

Toxicity	Follow-up Evaluation
Hematology	If \geq CTCAE Grade 3 neutropenia or \geq CTCAE Grade 3 thrombocytopenia have been demonstrated, these parameters must be repeated at least twice a week until resolution to \leq CTCAE Grade 1 or baseline to allow for initiation of re-treatment, and then at least weekly until either initiation of re-treatment or until stabilization.
Renal	If creatinine clearance (calculated or measured value) <30 mL/min has been demonstrated, this parameter must be repeated at least twice a week until resolution to baseline to allow for initiation of re-treatment, and then at least weekly until either initiation of re-treatment or until stabilization.
Hepatic	If bilirubin \geq 2×ULN or \geq CTCAE grade 3 ALT or AST or the combination of \geq CTCAE Grade 2 bilirubin and \geq CTCAE Grade 2 ALT or AST elevation has been demonstrated, assessment of these parameters must be repeated at least twice a week until resolution to \leq CTCAE Grade 1 or baseline to allow for initiation of re-treatment, and then at least weekly until either initiation of re-treatment or until stabilization.
	Patients with total bilirubin $>1.5 \times \text{ULN}$, or $>3.0 \times \text{ULN}$ for patients with Gilbert's syndrome (any duration) should have fractionation of bilirubin into total/direct or indirect/direct components and any additional work-up as clinically indicated by these results. Follow-up of hyperbilirubinemia should proceed as per the guidelines above, irrespective of the results of fractionation.
Cardiac	If at any time a QTcF >480 ms and \leq 500 ms is observed, a cardiology consultation must be sought to re-evaluate both baseline and abnormal electrocardiogram (ECG) finding to confirm the occurrence, severity, and causality of the AE.
	If at any time a QTcF >500 ms is observed, 1) Triplicate ECGs (2-3 minutes apart) need to be taken approximately 1 hour after the initial ECG. 2) If the mean QTcF is >500 ms, the patient must postpone study treatment until a cardiologist has re-evaluated the ECG. 3) The re-evaluation of ECG needs to be done as soon as practical but within 7 days of the initial abnormal ECG. 4) If the cardiologist confirms a mean QTcF >500 ms, the patient must be discontinued permanently from study.
Nonlaboratory	Patients who experience non-laboratory Grade 3 or 4 AEs must be evaluated at least once a week following demonstration of the resolution of the toxicity to allow for re-treatment, until stabilization of the toxicity, or until study completion.

Abbreviations: AE=adverse event; ALT=alanine aminotransferase; AST=aspartate aminotransferase; CTCAE=Common Terminology Criteria for Adverse Events; ECG=electrocardiogram; ULN=upper limit of normal

5.3.2. Dose and Schedule Modifications for Fulvestrant

The only dose modification for fulvestrant in the prescribing information (PI) is the recommendation for a reduction to 250 mg per IM injection for patients with moderate hepatic impairment (Child-Pugh Class B). A Child-Pugh score of 7 – 9 is deemed Class B, and is a composite of scores for total bilirubin, serum albumin, prothrombin time, ascites and hepatic encephalopathy (Appendix C).

5.4. Treatment Compliance

Each patient will be instructed to comply with the dosage and dosing regimen of TAS-120. Fulvestrant will be administered to patients in Cohort 4 only in the clinic under the supervision of clinic staff; all details of administration will be recorded in the eCRF.

Compliance with all study medication administration should be documented in the patient's source documents.

5.5. Concomitant Medications and Therapies

The following therapies are permitted:

- Bisphosphonates;
- Denosumab:
- Non enzyme-inducing anticonvulsants such as gabapentin, lamotrigine, and levetiracetam;
- Steroids for patients with brain metastases; and/or
- Local or regional palliative cryotherapy or radiation, such as for bone pain or palliative surgery (non-anti-neoplastic intent), provided this is not a site of measurable disease and is not indicative of disease progression.

If, after assessment by the Investigator, radiation for brain metastasis, therapy for bone metastasis, or locoregional therapy should be initiated for the best benefit of the patient, the patient may begin such therapy a minimum of 2 days after discontinuation of TAS-120. Consequently, the patient will be censored for the primary endpoint analysis. TAS-120 may be restarted 2 weeks after completion of such treatment or when the patient has recovered from the side effects of such treatment.

The following medications/therapies may be given concomitantly under the following guidelines:

Hematologic Support: may be administered as medically indicated (that is, blood transfusions, granulocyte colony-stimulating factor, erythropoietin stimulating agents) according to the institutional site standards or ASCO guidelines (Smith et al. 2015).

Management of Diarrhea: Prophylactic treatment for diarrhea is permitted during the study if clinically indicated according to the institutional or published guidelines (Benson et al. 2004).

Management of Nausea/Vomiting: Antiemetics may be administered as clinically indicated according to institutional standards or ASCO guidelines (Hesketh et al. 2017).

5.5.1. Drug Interactions

Drug interaction studies with TAS-120 have not been conducted in humans. The following information is based on results from *in vitro* studies. Caution is advised if these drugs are given concomitantly (see Appendix D, Classification of Substrates, Inhibitors, and Inducers of CYP Enzymes and Transporters).

Cytochrome P450 (CYP) 3A inhibitors and inducers: CYP3A is involved in the metabolism of TAS-120. CYP3A inhibitors and inducers may alter the concentration and activity of TAS-120.

CYP3A substrates: TAS-120 is a potential time-dependent inhibitor of CYP3A. TAS-120 may increase the concentration and activity of CYP3A substrates.

P-glycoprotein (P-gp) and breast cancer resistance protein (BCRP) substrates and inhibitors: TAS-120 is a substrate of P-gp and BCRP, and a potential inhibitor of P-gp and BCRP. TAS-120 may alter the PK and activity of P-gp and BCRP substrates. P-gp and BCRP inhibitors may alter the concentration and activity of TAS-120.

There are no known drug-drug interactions reported for fulvestrant (Fulvestrant PI).

5.5.2. Prohibited Medications and Therapies

Patients are not permitted to receive any other investigational or any other anticancer therapy, including chemotherapy, immunotherapy, biological response modifiers, or antineoplastic endocrine therapy during the study treatment period.

Extended-field radiation therapy or palliative radiation to a focal site of measurable disease is also prohibited. If it is deemed in the best interest of the patient and after discussion between the Investigator and Sponsor, it can be administered, but the patient will be censored for the primary endpoint analysis.

5.6. Effective Contraception During Study

Female patients considered not to be of childbearing potential must have a history of being postmenopausal (no menses for 12 months without an alternative medical cause), or hysterectomy that is clearly documented in the patient's source documents.

For WOCBP, including female study participants and partners of male participants, effective contraception is required during the study and for 90 days after the last dose of TAS-120 and 1 year after last dose of fulvestrant (Cohort 4 only). Effective contraception is defined as follows:

- Combined (estrogen and progestogen containing) hormonal contraception associated with inhibition of ovulation:
 - o oral
 - o intravaginal
 - o transdermal
- Progestogen-only hormonal contraception associated with inhibition of ovulation:
 - o oral
 - o injectable
 - o implantable
- Intrauterine device
- Intrauterine hormone-releasing system
- Bilateral tubal occlusion
- Vasectomized partner with documentation of the success of the vasectomy
- Complete abstinence from heterosexual intercourse (periodic abstinence is not a safe method)

Male patients with partners who are WOCBP should use a male condom in combination with at least one of the effective contraception methods for WOCBP during the study and for 90 days after the last dose of TAS-120 and 1 year after last dose of fulvestrant (Cohort 4 only).

Donation of sperm or ova is not allowed during the study and for 90 days following the last dose of TAS-120 and 1 year after last dose of fulvestrant (Cohort 4 only).

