Collectively, safety data from clinical trials suggest that TAS-120 is tolerable to patients with advanced cancers. The most frequently reported treatment-related adverse event (AE) overall has been hyperphosphatemia, mostly of National Cancer Institute – Common Terminology Criteria for Adverse Events (NCI-CTCAE) Grades 1-2 and without clinical complications. Other frequently reported treatment-related AEs included the gastrointestinal system disorders of diarrhea, dry mouth, nausea, and stomatitis. Dry skin and increased liver enzymes were also reported, most of which were mild to moderate in severity.

Safety concerns that have been identified from preclinical studies of TAS-120 include an increase of inorganic phosphorus in plasma, ectopic mineralization in various organs and tissues, lesions in bone/cartilage, and corneal lesions. An embryo-fetal developmental toxicity study conducted in rats showed that TAS-120 inhibited normal development of the rat embryo-fetus and resulted in embryo-fetal lethality. Effective contraception is mandated for any patients receiving TAS-120 who are of child bearing potential and their partners.

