- i. HR⁺ HER2⁻ breast cancer (defined as above) harboring an *FGFR1* high-level gene amplification as defined in Section 6.1.1.1
- ii. Measurable disease per RECIST 1.1
- iii. Has received 1-2 prior endocrine-containing therapies and no more than 1 prior chemotherapy regimen for advanced/metastatic disease. Prior treatment with fulvestrant is not permitted.
- iv. Has received prior treatment with a CDK4/6 inhibitor or is ineligible for such treatment (per Investigator decision)
- v. Pre/peri-menopausal patients must be on goserelin. Patients must have commenced treatment with goserelin or an alternative GnRH agonist at least 4 weeks prior to the first dose of fulvestrant. If patients have received an alternative GnRH agonist prior to study entry, they must switch to goserelin for the duration of the trial. Postmenopausal is defined as at least one of the following criteria: age ≥60 years; age <60 years and cessation of regular menses for at least 12 consecutive months with no alternative pathological or physiological cause; and serum estradiol and follicle-stimulating hormone level within the laboratory's reference range for postmenopausal females; or documented bilateral oophorectomy.
- vi. Has experienced disease progression/recurrence within 1 month following the completion of any endocrine therapy for advanced/metastatic breast cancer.
- 5. Archival or (preferably) fresh tumor tissue must be available for central laboratory confirmation of *FGFR* amplification.
- 6. The patient is able to take medications orally (a feeding tube is not permitted).
- 7. The patient has adequate organ function as defined by the following criteria:
 - a. Aspartate aminotransferase (AST) and alanine aminotransferase (ALT) \leq 3.0 × the upper limit of normal (ULN); if liver function abnormalities are due to underlying liver metastases, AST and ALT \leq 5 × ULN
 - b. Total bilirubin $\leq 1.5 \times \text{ULN}$ or $\leq 3 \times \text{ULN}$ in case of Gilbert's syndrome
 - c. Absolute neutrophil count (ANC) \geq 1.0 × 10 9 /L without hematopoietic growth factor support
 - d. Platelet count \geq 75 × 10⁹/L without transfusion support (that is, excluding measurements obtained within 3 days after transfusion of platelets)
 - e. Hemoglobin ≥9.0 g/dL without transfusion support (that is, excluding measurements within 7 days after transfusion of packed red blood cells or whole blood)
 - f. Serum phosphorus \leq ULN

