- g. Creatinine clearance (calculated or measured value): ≥40 mL/min
- 8. Women of child-bearing potential (WOCBP) must have a negative serum pregnancy test prior to administration of the first dose of TAS-120. Female patients are not considered to be of child-bearing potential if they have a history of hysterectomy or are post-menopausal, defined as above. Both males and females of reproductive potential must agree to use effective birth control during the study prior to the first dose and for 90 days after the last dose of TAS-120 and 1 year after last dose of fulvestrant (Cohort 4 only).
- 9. The patient is willing and able to comply with scheduled visits and study procedures.

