5.1.2. Fulvestrant

Fulvestrant (Faslodex®) will be administered to patients in Cohort 4 only according to the approved commercial labeling.

Fulvestrant 500 mg will be administered IM into the buttocks (gluteal area), slowly (1-2 minutes per injection), as two 5-mL injections, one in each buttock, on Days 1 and 15 of Cycle 1, then Day 1 every subsequent cycle thereafter (every 28 days \pm 3 days).

Pre/peri-menopausal patients in Cohort 4 are required to also have ovarian suppression with goserelin as part of standard of care, having started a GnRH analogue at least 4 weeks prior to the first dose of fulvestrant.

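### Section 5.6 accepts combined estrogen-containing contraception for all women of child-bearing potential, including pre/peri-menopausal HR+ women in Cohort 4, who must be on goserelin and receive fulvestrant

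*Protocol*

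**What the plan says.** **Contraception.** Protocol section 1.2.2, after describing embryo-fetal toxicity in rats, says "Effective contraception is mandated for any patients receiving TAS-120 who are of child bearing potential and their partners". Inclusion criterion 8 in section 4.1 turns this into an entry condition: patients of reproductive potential "must agree to use effective birth control during the study". Section 5.6 sets the scope, "For WOCBP, including female study participants and partners of male participants, effective contraception is required during the study", and then the content, "Effective contraception is defined as follows". The first item on the list is "Combined (estrogen and progestogen containing) hormonal contraception associated with inhibition of ovulation", by oral, intravaginal or transdermal route. The same section sets a longer contraception period for Cohort 4, one year after the last fulvestrant dose, so that cohort is plainly within its scope.

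**Cohort 4 treatment.** Criterion 4.D in section 4.1 restricts the cohort to HR+ HER2- disease and states "Pre/peri-menopausal patients must be on goserelin". Women who come in on another GnRH agonist are told that "they must switch to goserelin for the duration of the trial". Section 5.1.2 repeats the rule for the treatment period: these patients are "required to also have ovarian suppression with goserelin as part of standard of care", alongside fulvestrant 500 mg.

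**The concern.** The protocol does not leave ovarian suppression in Cohort 4 to local judgment. It names the agent, requires a GnRH agonist for at least 4 weeks before the first fulvestrant dose, and has a rule for switching agents. For the same women, section 5.6 names an estrogen-containing product as an acceptable way to meet a mandatory requirement, without any caution. The two rules pull in opposite directions.

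What is at stake is mainly participant protection. At about 75 sites, an investigator who accepts a combined product in such a woman commits no protocol deviation, and a monitor has no text on which to query it.

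**Working it through.** The check is textual; there is no figure in the plan to reproduce. There are three questions.

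**1. Does the list reach pre/peri-menopausal women in Cohort 4?** Under section 5.6 a woman is not of child-bearing potential only if she is postmenopausal (12 months without menses and no other medical cause) or has had a documented hysterectomy. A premenopausal woman on goserelin with an intact uterus meets neither condition. She is a WOCBP, must use effective contraception, and must take it from the list in 5.6. The list makes no distinction by cohort, receptor status or goserelin use.

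**2. Does another section take the method away?**

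| Place | What it restricts | Does it bar contraceptive estrogen? |
|---|---|---|
| 4.1, criterion 8 | Requires effective birth control | No method is excluded |
| 4.2, exclusion criteria | Medical history, prior therapy, fulvestrant hypersensitivity (Cohort 4) | No |
| 5.5, concomitant therapies | Lists permitted supportive and local therapies | Not mentioned |
| 5.5.1 and Appendix D | Caution with CYP3A, P-gp and BCRP agents | Contraceptives are not named |
| 5.5.2, prohibited therapies | Investigational and anticancer therapy, including endocrine therapy given against the tumor | No; a contraceptive is not given with that intent |
| SAP | Coding, summary and listing of concomitant medication | Not addressed |

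None of these overrides the explicit acceptance in 5.6.

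**3. What would a restriction remove?** Section 5.6 has seven method classes: combined hormonal, progestogen-only hormonal, intrauterine device, hormone-releasing intrauterine system, bilateral tubal occlusion, vasectomized partner, and complete abstinence. Excluding the combined class leaves 7 − 1 = 6, so contraception remains feasible for these women.

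**Size.** The affected group is WOCBP in Cohort 4 who would choose a combined method. The documents give neither the share of pre/peri-menopausal patients in the cohort nor any figure for contraceptive choice, so the number cannot be derived.

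**The case against.** The strongest reply is that the scenario is narrow. Section 5.6 is a shared list that also serves partners of male participants, for whom combined contraception raises no such issue. Cohort 4 has its own specific rule on ovarian suppression, and an investigator applying it may well not accept estrogen in an HR+ patient. Concomitant medications are recorded from consent to 30 days after the last dose (or the start of new anticancer therapy), and the SAP summarizes and lists them, so use would be visible. Exclusion criterion 15f lets the investigator refuse a patient whose condition may interfere with interpretation. This is fair, and it keeps the point small. It does not remove it: recording a drug is not barring it, and a discretionary exclusion does not cancel a method that the protocol names as acceptable.

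It is also correct that no passage says contraceptive estrogen is harmful in these patients. The conflict is an inference from the protocol's own suppression requirement.

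A reader might infer more than the documents support:

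- *That the list applies to all female participants.* It applies to WOCBP; postmenopausal women and women with a hysterectomy are outside it.
- *That up to 34 of 168 patients are affected.* The 34 is the planned maximum for Cohort 4, reached only if 20 mg is not tolerated in the safety lead-in; otherwise the plan is 28. It counts postmenopausal women, women with a hysterectomy and any men. It does not measure this problem.
- *That 6-month PFS is compromised.* Nothing in the documents gives a rate of use or an effect of such use.
- *That the same conflict exists in Cohorts 1 and 3.* HR+ women there may use the same list, but the protocol requires neither goserelin nor fulvestrant of them, so the internal contradiction does not arise.

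**Conclusion.** The point holds as a small inconsistency in participant protection, worth correcting because correction is cheap. Section 5.6 explicitly accepts an estrogen-containing method for women whose mandated treatment suppresses ovarian estrogen, and no other text withdraws that acceptance. This is a stated rule that conflicts with another stated rule, rather than a detail left out.

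It rests on two readings: that a premenopausal woman on goserelin without hysterectomy is a WOCBP under 5.6, and that supplying estrogen runs against the purpose of ovarian suppression. The first follows from the text; the second is an inference. The number affected is not derivable, and no effect on the primary endpoint, the design or the analysis is claimed.

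One separate editorial note adds no weight to this. Criterion 8 in the synopsis and section 5.6 define postmenopausal as 12 months without menses. Criterion 8 in section 4.1 refers back to the definition in 4.D.v, which also admits age 60 or over alone and bilateral oophorectomy and, on the natural reading, asks amenorrheic women under 60 for hormone confirmation. A woman at the margin can therefore be a WOCBP in one section and not in another.

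**What to change.** Add one sentence to section 5.6: *Estrogen-containing hormonal contraception is not acceptable for female participants of child-bearing potential in Cohort 4.* It should apply at minimum while the woman is on goserelin and fulvestrant. The sponsor should state whether it also covers the contraception period of up to one year after the last fulvestrant dose, when the suppression argument no longer applies directly. Leave the list as it is for partners of male participants.

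The cost is one sentence in the next amendment and matching consent wording. The downside is one fewer method class for these women, six instead of seven. Sample size and analysis do not change. Whether to restrict progestogen methods in Cohort 4, or hormonal methods for HR+ women in Cohorts 1 and 3, is a question for the sponsor and not part of this change.

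As a separate editorial item, use one WOCBP definition in synopsis criterion 8, criterion 8 of section 4.1 and section 5.6, and keep 4.D.v for deciding who needs goserelin. If hormone confirmation goes into the common definition, amenorrheic women under 60 outside Cohort 4 would need estradiol and FSH tests to be classed as not of child-bearing potential.
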